8.1. Driving of the samples

The samples will be stored in the laboratories of each center and will remain there until the end of the test. The handling of samples will be carried out according to the usual clinical practice of each center where the test is carried out.

Terms for the shipment of medication

The coordinating center will be responsible for sending the medication to the different centers participating in the trial. Special precautions for storage will be maintained to maintain optimal conditions and preserve the stability of the medication, as stated in the technical data sheet.

8.2. Variables to study

- Measurement of the anti-HBs antibody titer: before the first dose and one month after the administration of each dose.
- Pickup of adverse effects during administration and all those that could be

related to the vaccine and that appear within 30 days after each dose.

9. Statistical analysis

A statistical analysis of the data will be carried out, assisted by the IBSAL Biostatistics Research Group

- Sample size justification**

The sample size is based on the recruitment carried out from the previous study carried out at the Salamanca University Healthcare Complex. Considering the number of subjects susceptible to study in the different centers, a sample size of up to 80 subjects is estimated.

- Statistical methodology**

The results of the present trial and the clinical-biological data of the patients will be registered in a database.

Statistical significance: The results will be analyzed using SPSS software (version 15.0) for Windows.

An initial descriptive analysis of the quantitative variables will be carried out, which will include measures of central tendency (mean, median), measures of dispersion (range, standard deviation) and box plots, with possible extreme values. For qualitative variables, frequencies will be presented.

The level of significance will be set at $p < 0.05$.

10. Ethical aspects and legal

The researcher will carry out the study in compliance with the ethical principles of the Declaration of Helsinki.

The trial must adhere to the protocol, which guarantees compliance with Good Clinical Practices, described in the Harmonized Tripartite Guidelines of the ICH on Good Clinical Practices.

This trial will be submitted for evaluation by a Drug Research Ethics Committee and the Spanish Agency for Medicines and Health Products (AEMPS) will be notified.

The pertinent authorizations will be obtained in accordance with current regulations for clinical trials.

- Information sheet and consent form**

The researcher will explain to each patient (witness or legal representative) the nature of the trial and the purposes, procedures, estimated duration, possible risks and benefits of participating in the trial and possible inconveniences that it may cause. All patients will be informed of the voluntary nature of their participation and that they may withdraw at any time, without affecting their future medical care or their relationship with the doctor responsible for their treatment.

The patient will have sufficient time to read and understand the explanations included in the patient information sheet (Annex 2) before giving their informed consent (Annex 2). No patient may be included in the trial before having obtained their

informed consent.

- **Protection of personal data**

The confidentiality of individual patient data will be always respected. The original data will be kept in the corresponding Service and only the trial researchers or inspectors will have access to them, in the event of inspection by the Spanish Health Authorities.

The patients will be identified by a patient code. The researcher will inform the patients that the data obtained during the trial will be stored and analyzed by computer, in compliance with Regulation (EU) 2016/679 of the European Parliament and of the Council, of April 27, 2016, regarding the protection of natural persons about the processing of personal data and the free circulation of these data and to LO 15/1999, of December 13 on Protection of Personal Data.

The researcher is the only person who can and should know the origin of the data obtained and who can associate them with the patient.

Personal data (full name, address, place of work, NIF) of the researchers will be recorded in a computerized file, with the sole purpose of facilitating the organizational and logistical aspects necessary for the development of the trial.

In compliance with the afore mentioned regulations, the data file will be treated confidentially, and the researchers may exercise their rights of access, rectification, cancellation, and opposition regarding the registered personal data, if they request it by writing to the Delegate of Data Protection of the promoter at [contact]

- **Interference with the doctor's prescription habits.**

Patients included in the trial must meet the inclusion and exclusion criteria detailed in the protocol. Based on the trial inclusion and exclusion criteria, researchers will only include patients for whom the study drug prescription is appropriate. As specified in Section 7, the doctor may suspend the treatment at any time during the follow-up and replace it with another drug that he considers more beneficial for the patient.

- **Responsibilities of all trial participants**

Investigator

The investigator must meet the following requirements:

- Engage to carry out the test as stipulated in the protocol.
- Report to trial patients and obtain their consent.
- Get, register, and report the data correctly, responding, if applicable, to its validity and quality in the audits.
- Facilitate audits and inspections by health authorities. Therefore, after submitting the final report, you should keep the trial documentation for at least 5 years.
- Know how to explain the objectives, the basic methodology and the meaning of

the test results to the scientific and professional community.

- Notify your participation in the test to those responsible for the management of your center.
- Make sure that the information recorded in the ECRF is accurate and correct, and that it has been obtained as indicated in the protocol.
- The researcher is the only person who can and should know the origin of the data obtained and associate them with the patient, ensuring that no extra (unsolicited) information appears in the ECRF that could identify the patient (name, PASSPORT NUMBER, SOCIAL SECURITY AFFILIATION NUMBER, address, telephone, etc.).
- Specifically, the researcher must guarantee the best possible care for the patient, always putting their well-being and safety first.

Coordinating researcher

The coordinating investigator must meet all the investigator requirements of the trial and sign the protocol and possible amendments, together with the sponsor; will be jointly responsible, together with the promoter, for the drafting of the final reports; help to disseminate the results of the trial in collaboration with the sponsor; undertake not to sign any contract that contains confidentiality clauses on future trial results and not to disclose the results of the trial, avoiding at all times jeopardizing the integrity of the trial (for example, by publishing partial results of an investigator or a center).

Monitor

Will does the functions contained in Royal Decree 1090/2015. From December 4, which regulates the clinical trials with drugs, the Ethics Committees for Drug Research and the Spanish Registry of Clinical Studies. The Sponsor has delegated the monitoring functions of the trial to the SCReN platform of the Carlos III Health Institute.

Head of the Pharmacovigilance Node

The Sponsor has delegated the monitoring functions of the trial to the SCReN platform of the Carlos III Health Institute.

Following SCReN's SOP-PFV 2, 3, 4, 5, 6, 7 procedures, your responsibilities will be:

- Receive by Fax or email from the researchers, and sign the information received. Check that AGA / pregnancy meets severity criteria, reflects intensity, investigational drug, causality assessment, and investigator signature. In the case of any blank data, the person in charge of Pharmacovigilance or person delegated, will immediately contact the center for immediate correction.
- Give a number to the notification of SAE / pregnancy and send it to the investigator (only in the first communication of the case)
- Review the information on the SAE / pregnancy received. It must be completely and medically consistent. Additional information may be required (queries or discrepancies).
- Send a copy (fax or email) of the receipt form or the queries / discrepancies to the CRA or the project manager or the Promoter.

- Register the cases individually in a database.
- Determine the predictability of the AGA / pregnancy received.
- Contact the promoter or coordinating researcher to report the AGA / pregnancy received and the causal relationship made by the notifier.
- Request from the promoter the confirmation of the causality and predictability of the AGA / pregnancy carried out by the Pharmacovigilance Node.
- Notify the researchers, Health Authorities (AEMPS and CCAA), the RAGIS received.
- Archive all generated documents. *

* Only AAs notified as serious and unexpected, and related to medication (RAGI), are sent to the competent authority. For this, the official form will be used. The RAGI will notify the AEMPs at [contact] and the Autonomous Communities via mail electronic, but not to the CEIm.

Promoter

The promoter:

- It will be responsible for ensuring compliance with the relevant legislation.
- He will sign the protocol and possible amendments, together with the coordinating researcher.
- Will present the protocol to the CEIm.
- Will present the trial protocol and the final report within the established deadlines and, if necessary, will communicate the interruption of the trial and the reasons that have motivated it.
- Identify sources funding for the trial.

- Ethics Committee for Drug Research **(CEIm)**

The Ethics Committee for Drug Research (CEIm) will review the protocol, the proposed informed consent form and other information for patients. Any modification of the protocol, apart from administrative changes, will require an amendment to the protocol that must be approved by said Committee. Changes in the direction of the trial that are not accompanied by an amendment will be considered deviations. Deviations may lead to disqualification of the center from continuing to participate in the trial.

11. Practical considerations

- **Study plan and inclusion of patients**

The patients will be selected and, once informed consent has been obtained and verified that the patient meets the selection criteria, the information will be recorded in the ECRF and the samples provided will be analyzed.

- **Procedures for the communication of adverse reactions**

An adverse event is the appearance of signs, symptoms, or an undesirable medical pathology (or the worsening of the pre-existing ones) that occurs after the signing of the informed consent, even if the event is not considered related to the treatment.

An adverse drug reaction is the appearance of signs, symptoms, or an undesirable medical condition in a patient receiving a drug that is considered drug related.

Serious adverse event

To ensure patient safety, any serious adverse event (SAE), regardless of suspected causation, that occurs after the patient has given informed consent and up to 4 weeks after treatment / patient participation has been discontinued. the trial, the researcher will send the completed SAE / pregnancy form (Annexes 4 and 5), in the first 24 hours from its knowledge to the Pharmacovigilance Node (UICEC Hospital Universitario de Canarias). [contact] or by email to: [contact]. . The original and duplicate copies of the SAE Form, and the fax confirmation sheet, will be kept at the trial site, along with the data collection notebooks.

ASAE is defined as an event that:

- Cause death or life threatening.
- Causes a disability/ persistent or significant disability.
- It constitutes a congenital anomaly / birth defect.
- Requires hospitalization or the prolongation of a pre-existing hospitalization, unless the hospitalization is due to:
 - to routine treatment or to the control of the studied indication, without deterioration of the pathology (specify what it includes)
 - elective or previously planned treatment of a pre-existing pathology not related to the indication studied and that has not worsened since the beginning of the administration of the drug of interest.
 - to social reasons or temporary care of the patient, in the absence of deterioration of the general condition of the patient
- It is medically significant, that is, it is defined as an event that compromises the patient or may require medical or surgical intervention to prevent any of the above-mentioned outcomes.
- Outpatient treatment emergency for an event that does not meet any of the above definitions of SAE and does not result in a hospital admission.

Serious adverse events occurring more than 4 weeks after study withdrawal will only be reported to the Sponsor according to the procedures established in this protocol for other serious adverse events, if the investigator suspects that there is a relationship with the study treatment.

To the extent possible, all SAEs will also be described by (but not only):

- its duration (start date = date of first signs or symptoms) and end date
- severity and intensity criteria, if applicable (mild, moderate, severe)

- their relationship with current investigational drug (suspected / not suspected, investigator judgment),
- the action or actions taken and the results of your investigation, if applicable
- details of concomitant medication
- outcome

The follow-ups of the SAE will follow the same form indicating follow-up and its shipment must be made within 7 days, (stating that it is the “follow-up” form). The follow-up report will indicate if the event has been resolved or is still active, if and how it has been treated and if the patient's participation in the trial has continued or ended. The trial site will keep the form and the fax confirmation sheet.

To ensure the safety of female patients, pregnancies in participating patients will be reported within 24 hours of knowledge. The pregnancy will be recorded in a Pregnancy Form and the researcher will notify the Pharmacovigilance Node (UICEC Hospital Universitario de Canarias). [contact] or by email to: [contact] .. Pregnancy monitoring will be recorded in the same form and will include an assessment of the possible relationship between the outcome of the pregnancy and the drug under study. Any SAE that occurs during a pregnancy will be reported using the SAE Notification Form.

Adverse event

Adverse Events must be included in the relevant section of the ECRF - Adverse Event- describing the following parameters:

- Description of the Adverse Event.
- Start date.
- Has treatment finished?
- Relationship with medication (possibility of adverse reaction)
- Action taken with the Investigational Drug.
- Intensity of the event - Grade CTCAE-.
- Concomitant treatment administered.
- Resolution.

- **Registry of data and preservation of documentation**

The researcher will fill in all the data in the ECRF following the guidelines indicated for said completion and will report all the data according to the procedures specified by the sponsor at the beginning of the trial.

Patient data collected in the ECRF during the trial should be documented anonymously; patients will only be identified by the patient code. All the information registered in the ECRF must be verifiable from the original documents of the patient's medical history.

The researcher will keep the original documents necessary for possible inspections by the health authorities for a period in accordance with current legislation.

The ECRF data will be entered into a trial database, through simple entry. The

information entered will then be systematically verified.

- **Periodic safety reports (DSUR)**

Following the rules of good clinical practice, current regulations, and SCReN's SOP-PFV 11 procedure, the Pharmacovigilance Node will have a safety report prepared once a year (SOP-PFV 11 / 01.1 Format). This report will contain the safety evaluation of the drug in accordance with all the SAEs received by the person in charge of Pharmacovigilance of the Node.

The person in charge of the Pharmacovigilance Node will send the DSUR to the Project Manager for review, indicating the need to receive a response within a maximum period of 15 days and the deadline.

The person in charge of the Pharmacovigilance Node will then send the DSUR to the Promoter for approval, indicating the need to receive a response within a maximum period of 15 days and the deadline.

All modifications suggested by the GP or the promoter will be carried out by the Head of Pharmacovigilance.

The latest version of the DSUR will be signed by the Head of PV of the Node, then by the GP (as reviewer) and finally by the promoter granting their approval.

The annual safety report (DSUR) will be sent by the promoter to:

- AEMPS: via ECM portal using "E iv) Annual safety report (DSUR) [AEMPS only]"
- CEIm of the Salamanca Health Area: via ECM portal using "E ii) Report on the progress of the trial."
- Contact points in clinical trials of the Autonomous Communities via email. (Annex 3: Annex 2 of the AEMPS Instructions)

The Project Manager will send the Pharmacovigilance Node a copy of the acknowledgment of receipt from the AEMPS.

- **Reports follow-up and conclusion**

The Promoter, in accordance with the current regulations and instructions that regulate clinical trials by the AEMPS, will send the pertinent monitoring reports.

Three months after the completion of the inclusion of patients, a statistical report will be drawn up that will include all the results of the study. This report will be made known to the participating researcher. In addition, copies of the report will be sent to the CEIm that has evaluated the study and to the AEMPS.

Any report obtained from this study will be considered confidential, at least until the person responsible for the study has reviewed and analyzed it. The data set can be used for general publications, which should always refer to the study. The researcher agrees not to provide information related to the study or provide access to their data to third parties.

- **Disclosure of results**

Independently of the results of the study, the promoter agrees to present them to the

medical community through scientific publications, conferences, or other means. Any formal presentation or publication of study results will be considered a joint publication of the investigator (s) and the sponsor.

12. Practical utility results in relation to health

Relevance of the projects for its impact

- 1) clinical, healthcare and / or technological development.
- 2) bibliometric.

1) Fendrix® is a hepatitis B vaccine that contains a new adjuvant that has a higher immunogenic capacity than the conventional vaccine. For this reason, although its use is only authorized in patients with renal failure, it is intended to initiate a protocol for use outside the technical data sheet for its use in health workers who have not responded to two complete vaccination guidelines.

There must be considered that post-exposure prophylaxis with specific immunoglobulin should be done in non-responders. The recommended guidelines according to the technical data sheet are:

- Single dose 12-20 IU / kg (administered as soon as possible).
- Two doses, one during the first 24 hours and another a month.

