For its part, Directive 2010/32 / EU of May 10, 2010, which applies the Framework Agreement for the prevention of injuries caused by sharp instruments in the hospital and health sector and article 6 of Order ESS / 1451/2013, of July 29, which transposes the previous Directive, establishes that "vaccination must be offered free of charge to all workers and students who carry out health and related activities in the workplace": In the case of not acceptance of the offered vaccination must be recorded in writing of this decision.

The inclusion of this population of university students will be subject to the specific instructions on occupational prevention in each autonomous community. In the case of centers located in the Community of Castilla y León, their inclusion will be made based on the document "Instructions of the Ministry of Health of the Junta de Castilla y León of October 11, 2013" (link: http://www.sanidad.ccoo.es/comunes/recursos/15617/doc287408_Instruccion_de_la_gerenciaRegional_de_Salud_sobre_adopcion_de_medidas_de_prevencion_de_riesgos_y_salud_laboral_para_los_estudiantes_que_realizan_sus_practicas_df_que_realizan_sus_practicas_df

Therefore, it is proposed to carry out a broader study involving as collaborators several hospitals belonging to the NHS and the expansion of the target population.

5. goals

- **Main goal**

1. Benefit and equip NHS staff with an additional protection tool against hepatitis B infection.
2. To evaluate the efficacy of the adjuvanted vaccine in healthy subjects NON-responders to the conventional hepatitis B vaccine.

- **Secondary objectives**

1. Analyze results of anti-HBs antibody titers to see the immune response to the adjuvanted vaccine.
2. Evaluate safety results and clinical tolerance of the adjuvanted vaccine.

6. Source and information field

The source and field of information will be the electronic data collection notebook (ECRFe) that the researcher will fill in based on the patient's medical history.

7. Trial Design

- **Design:** open, multicenter clinical trial with use of off-label medication.
- **Duration:** 2 years
- **Ambit study:** Services of Prevention of Occupational Risks of the public hospitals of the NHS

The multicenter trial will be carried out in the following hospital centers:

- University Clinical Hospital from Valladolid. ([name] [name])
- Healthcare Complex of Zamora. ([name] [name])
- University Healthcare Complex of Lion. ([name] [name])

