Although the patient is not obliged to provide any explanation for leaving the trial prematurely, the investigator will reasonably attempt to determine the patient's motives, always respecting their rights. If a patient leaves the trial prematurely, the final visit data will be recorded in the ECRF.

The doctor may suspend the treatment at any time during the follow-up and replace it with another drug that he considers more beneficial for the patient, immediately informing the promoter of the trial.

• Treatment description and definition of exposure

Product description:

Fendrix® is a hepatitis B vaccine that contains HBsAg adjuvanted by 3-O-desacyl-4'-monophosphoryl lipid A and with aluminum phosphate. This adjuvant system is called AS04C and increases the immunogenicity of the vaccine.

- Generic name: Vaccine of Hepatitis B adsorbed and adjuvanted by AS04C
- Trade name: Fendrix®
- Laboratory: Glaxo Smithkline
- ATC therapeutic group: J07BC (Hepatitis Vaccines)
- Form of presentation: 20 µg pre-filled syringes

Fendrix® is a hepatitis B vaccine that contains HBsAg adjuvanted by 3- O-desacyl-4'-monophosphoryl lipid A and with aluminum phosphate. This adjuvant system is called AS04C and increases the immunogenicity of the vaccine. An anti-HB antibody titer \geq 10 mIU / mL correlates with protection against HBV infection. It is indicated for active immunization against infection by all known subtypes of Hepatitis B virus in patients with renal failure (including pre-hemodialysis and hemodialysis patients) older than 15 years. However, it is intended to take advantage of the greater immunogenic capacity

of this vaccine in non-responders, understood as those who have received two complete vaccination schedules without reaching an antibody titer greater than 10 mIU / mL.

Terms of administration:

Immunization will consist of a maximum of 4 doses of 0.5 ml administered according to the following schedule: 1 month, 2 months and 6 months from the date of the first dose, with an intramuscular vial in the deltoid muscle at the dose of 20 μ g, as stated in the Fendrix technical data sheet. After the administration of each of the doses, a serological analysis will be carried out (approximately 30 days after the administration of each dose), making it clear that if seroprotection is achieved (anti-HB \geq 10 mIU / ml, the administration will be suspended. of successive doses.

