The precautionary measures regarding contraindications and warnings of the product, recommended by the manufacturer and in accordance with the recommendations of the AEMPS for its use outside the technical data sheet, will be observed.

• Stages developmental

Stage 1:

- Start up:
 - Elaboration of the documentation of the final trial: latest version of the Protocol, Electronic Data Collection Notebook (ECRFe), Informed consent for the subject, etc.
 - Request to the AEMPS classification of clinical trial and recommendations for the use of the drug outside of the technical data sheet.
 - Obtaining of CEIms authorizations and necessary contracts with the centers: carried out by the Salamanca Hospital and the IBSAL (Technical Management Unit of the Salamanca Biomedical Research Institute-clinical trials area).
- Preselection of candidates (8 weeks) in the collaborating centers of:
 - Valladolid University Clinical Hospital.
 - Zamora Healthcare Complex.
 - León University Healthcare Complex.
 - Palencia University Healthcare Complex.
 - Salamanca University Healthcare Complex.

Pre-select the workers described in the target population based on the records obtained from their clinical-working histories, which have received 6 doses of conventional hepatitis B vaccine and have not exceeded 10 mIU / mL. Detection of new cases at the University Hospital of Salamanca.

Stage 2:

- Purchase of medication: coordinated from the IBSAL-Hospital de Salamanca.

- Transport of medication to the collaborating centers: from a commercial provider to the Occupational Risk Prevention Services of the participating centers.

Stage 3:

- Inclusion of participating subjects: recruitment in each center. Select the workers described in the target population based on the records obtained from their clinical-working histories, who have received 6 doses of conventional hepatitis B vaccine and have not exceeded 10 mIU / mL.
- Dosage administration, evolution monitoring and safety: Once the consent of the participant has been obtained, Fendrix® will be prescribed at a dose of 20 micrograms up to a maximum of 4 doses. The antibody titer per month of each dose of vaccine administered will be subsequently analyzed locally at each center. Possible events and adverse reactions will be detected, subsequently monitoring the applicable Pharmacovigilance.

Visits calendar from the patients:

Visits	Selection Visit	Visit1	Visittwo	Visit3	Visit4	Final visit

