Time		Month0	Month1	Month 2	Month6	Month7
Procedures and tests						
Pick up of data and tests required for the test	X					
Analytics	X		X	X	X	X
Drug administration		X	X	X	X	
Pick up of data related to other medications and adverse events		X	X	X	X	X
Completion sheet						X

Stage 4:

- Compilation of the analyzes and ECRFs from the collaborating centers to the coordinating center.
- Treatment of data and statistical analysis: coordinating center-IBSAL.

Stage 5:

- **Publication:** from the coordinating center.

- **Schedule. Plan of work**

Activity:	People involved	From (mm / yyyy)	Until (mm / yyyy)
Stage 1	8	Jan-2017	Dec-2018
Stage 2	6	May-2017	Feb-2019
Stage 3	8	Jun-2017	Jun-2019
Stage 4	7	Dec-2018	Dec-2019
Stage 5	6	Jan-2019	Apr-2020

- **Available media to carry out the test.**

The infrastructure where it will be carried out resides in the prevention services of the hospitals involved. In addition to the management support for its development by IBSAL in its Technical Management Unit (HU Salamanca). In these services there are adequate facilities, material means to carry out all the processes required for the development of the test (refrigerators, determinations of Ab, etc.)

The personnel involved in the trial are NHS personnel with extensive experience in Occupational Risk Prevention in the health field, in addition the trial will receive the necessary administrative management support from the Clinical Trials Area of the IBSAL Technical Management Unit

- **Limitations of the trial**

The main limitation of the trial will be to find new cases of non-responding workers and overcoming the difficulties of the lack of standardized records of non-responding workers from the different prevention services of the collaborating hospitals.

8. Valuation criteria and measurement instruments

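### The visit calendar has no Month 3 sample, so a site following it measures the dose-3 anti-HBs response about four months after the dose instead of the one month the text requires

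*Combined protocol and SAP*

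**What the plan says.** Three places in the protocol set the timing of the post-dose titre, and they agree:

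- Section 8.2: "Measurement of the anti-HBs antibody titer: before the first dose and one month after the administration of each dose".
- Section 7, Terms of administration: serology "approximately 30 days after the administration of each dose".
- Section 7, Stage 3: a titre at one month for each dose given, analysed locally. The translated sentence is awkward, but this is its natural reading.

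Terms of administration allows at most four doses: the first, then "1 month, 2 months and 6 months from the date of the first dose". It also ties dosing to the titre. Once anti-HBs is at or above 10 mIU/mL, "the administration will be suspended. of successive doses".

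The visits calendar in section 7 has a selection visit, Visits 1 to 4 and a final visit. Its last three columns are "Visit3 Visit4 Final visit", timed at "Month 2 Month6 Month7". Drug administration is marked at Months 0, 1, 2 and 6, and analytics at selection and Months 1, 2, 6 and 7. There is no Month 3 column.

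**The concern.** The text and the calendar cannot both be followed for dose 3. A centre that keeps to the calendar breaks the one-month rule. A centre that keeps to the text needs a visit the calendar does not contain. With five centres, practice could differ between them.

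Two things are at stake. First, the titre decides treatment: under the calendar, whether dose 4 is given depends on a value about 3 months later than the text intends. Second, the value recorded as the response to dose 3 has a different time since dose from those recorded after doses 1, 2 and 4. That matters for any description of response by dose under the secondary objective to "Analyze results of anti-HBs antibody titers to see the immune response to the adjuvanted vaccine".

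**Working it through.** The plan states no figure for this point, so the check is schedule arithmetic. The inputs are dose months 0, 1, 2 and 6 (Terms of administration and the calendar's drug row), the one-month rule (section 8.2, Terms of administration, Stage 3), and post-dose sampling at Months 1, 2, 6 and 7 (the calendar's analytics row).

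Required sample month = dose month + 1. Calendar interval = next analytics month − dose month.

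| Dose | Given at month | Titre due | Next calendar titre | Interval | Late by |
|---|---|---|---|---|---|
| 1 | 0 | 0 + 1 = 1 | 1 | 1 − 0 = 1 | 0 |
| 2 | 1 | 1 + 1 = 2 | 2 | 2 − 1 = 1 | 0 |
| 3 | 2 | 2 + 1 = 3 | 6 | 6 − 2 = 4 | 6 − 3 = 3 |
| 4 | 6 | 6 + 1 = 7 | 7 | 7 − 6 = 1 | 0 |

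Samples for a four-dose subject:

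- Text: pre-dose plus Months 1, 2, 3 and 7 = 5.
- Calendar: selection plus Months 1, 2, 6 and 7 = 5.
- In common: 4. Month 3 is only in the text and Month 6 only in the calendar.

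The equal totals make the mismatch easy to overlook.

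This is not a fault of the text extraction. The calendar has six columns, and the only blank in its analytics row is at Month 0.

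Consequences by titre in dose-3 recipients:

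| Month 3 | Month 6, before any dose 4 | Stopping rule on Month 3 | Stopping rule on Month 6 |
|---|---|---|---|
| ≥ 10 | ≥ 10 | stop | stop |
| < 10 | < 10 | dose 4 | dose 4 |
| ≥ 10 | < 10 | stop; responder to dose 3 | dose 4; recorded as not responding to dose 3 |
| < 10 | ≥ 10 | dose 4 | stop |

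Only the last two rows differ. The documents do not give the share of subjects still below 10 after two doses, so the number reaching dose 3 can only be bounded between 0 and the maximum enrolment of 80. The number crossing 10 between Months 3 and 6 cannot be estimated.

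The earlier compassionate-use study in section 4 shows that waning below 10 can occur. Of 20 subjects, 19 were protected at two months. At one year 15 were protected, three were below 10 and two were not followed. Both of those two had responded, so 19 − 2 = 17 responders were followed. At most one of the three low values can belong to the single early non-responder, so at least 3 − 1 = 2 of the 17 had fallen below 10. That study used a 40 µg regimen at Months 0, 1 and 6 over a longer interval, so it gives no rate for this trial.

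**The case against.** The best case against is that this is a calendar slip with little effect. Three statements support the one-month rule and one table departs from it, so a site reading the text would draw at Month 3 anyway. Dose 4 is due at Month 6 under either schedule, so no dose is delayed, and a Month 6 titre is current for the question of whether the subject is protected on that day. These points stand and limit the size of the problem. They do not remove it: no supplied text says which schedule prevails or provides an unscheduled Month 3 draw, and the calendar is the working tool at the sites. The electronic data collection manual (Annex 6) is a separate document that was not available and might settle it.

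A reader might infer several stronger things that the documents do not support:

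- *That drawing the titre at the next dosing visit is peculiar to dose 3.* It is not. Months 1 and 2 also have sampling and dosing at the same visit. Only the interval differs.
- *That the sponsor chose a four-month interval.* Nothing in the plan says so. It reads as an inconsistency.
- *That a planned by-dose analysis is spoiled.* The secondary objective does not mention analysis by dose. Section 9 plans "measures of central tendency (mean, median), measures of dispersion (range, standard deviation) and box plots" for quantitative variables in general. The by-dose use is an inference. Titres by dose would in any case describe a selected group, because subjects at or above 10 stop, and a Month 3 sample would not change that.
- *That the calendar contradicts the 30-day adverse-effect window.* Section 8.2 defines when an effect must appear, not when a visit must occur, and Month 6 collects adverse events.
- *That the overall response result is unsound.* A subject at or above 10 at Month 7 counts as a responder under either schedule.

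**Conclusion.** The inconsistency is real and should be fixed. One of four post-dose titres falls about 4 months after the dose under the calendar, against about 1 month in the text, and the dose-4 stopping decision then rests on it. This assumes that a site follows the calendar and that no document outside those supplied adds a Month 3 draw.

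The effect is confined to dose-3 recipients and to the timing and attribution of response. The main case is a subject at or above 10 mIU/mL at Month 3 and below 10 at Month 6, who would be recorded as not responding to dose 3 and given dose 4. Overall response by Month 7 is largely preserved. A responder would be lost only if a subject at or above 10 at Month 3 were below 10 at both Month 6 and Month 7.

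**What to change.** Add a Month 3 column to the visits calendar, with an anti-HBs sample for subjects who received dose 3. State that this titre is the post-dose-3 response and that it governs the stopping rule in Terms of administration: at or above 10 mIU/mL, no dose 4. If a Month 6 sample is kept, label it a pre-dose-4 titre and do not use it as the dose-3 response.

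The cost is one calendar amendment and one short visit per dose-3 recipient, at most 80 × 1 = 80 visits. The text already requires the Month 3 draw. Keeping Month 6 as well takes a four-dose subject from 5 samples to 6. Sample size is unchanged. Compared with following the calendar, the dose-4 decision changes only for subjects on different sides of 10 at Months 3 and 6.

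The alternative of rewriting the text to accept Month 6 would save the visit. It would mean changing the rule in three places and would leave the dose-3 response measured at a different interval from the others.
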